7.2.1.1 Screening Visit

This visit is applicable for all patients.

ACTIVITIES AND ASSESSMENTS:

- Informed Consent, *Section 13.1.3*
- Demography, *Section 10.4.1*
- Medical and Surgical history, *Section 10.4.2*
- CT Scan to be done within 3 weeks from Screening Visit unless a CT scan has been performed in clinical routine within 6 weeks prior to Screening Visit, *Section 10.4.3*
- Brain imaging (preferably by contrast-enhanced) Magnetic Resonance Imaging (MRI) or CT to be done within 3 weeks from Screening Visit unless a CT scan has been performed in clinical routine within 6 weeks prior to Screening Visit, *Section 10.4.3*
- Prior Medication, *Section 10.4.4*
- Physical Examination, *Section 10.5.3*

- Vital Signs, *Section 10.5.4*
- ECG, *Section 10.4.5*
- Laboratory Safety Blood Assessments: Hematology, Clinical Chemistry including Glomerular Filtration Rate (GFR) based on Creatinine (Creat), Glucose (Gluc), Thyroid stimulating hormone (TSH), Thyroxine (free T4), and Prothrombin Time - International Normalized Ratio (PT-INR), Activated Partial Thromboplastin Time (APTT), and Pregnancy *Section 10.5.5*
- Laboratory Safety Urine Assessments, *Section 10.5.5*
- Additional Laboratory Blood Assessments: Serology (HIV, HBV, and HCV), *Section 10.4.6*, High resolution tissue typing of Human Leukocyte Antigens (HLA), *Section 10.4.7*
- ECOG score, *Section 10.2.3.1* and Karnofsky performance status, *Section 3.2*
- █████ *Section 10.2.3.2*
- Inclusion/Exclusion Criteria, *Section 8.2* and *Section 8.3*. To be checked when the results from all assessments made at Screening are available.
- Randomization, *Section 9.2*. To be done when eligibility has been confirmed.
- Confirmatory diagnostic biopsy in accordance with local routines prior to Vacc1 Visit, if required by local regulations and laws, *Section 9.2*.
- AEs, *Section 11.2*

A telephone contact will be made with the patient once randomization has been done in order to inform about which treatment the patient was allocated to and for scheduling the next study visit and a confirmatory biopsy if applicable.

Extra consent for vaccination for patients randomized to the vaccine arm, to be taken after randomization if required by local regulations.

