7.2.1.10 Post-Study Survival Information

This measure is applicable for all patients.

- Survival data, *Section 11.3*

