8.5 Removal of Patients from Therapy or Assessment

Patients are free to discontinue their participation in the study at any time. Withdrawal from the study will not affect or prejudice the patient's further care or treatment. Patients may be withdrawn from study treatment and assessments at any time, if deemed necessary by the Investigator.

Patients who discontinue treatment with Intuvax and/or sunitinib for safety reasons (including DLT, see *Section 11.5*) or due to concomitant medication (*Section 9.6*) will not necessarily be considered withdrawn from the study unless there are other reasons for withdrawal. They should return for all following visits and assessments until PD.

Examples of reasons for withdrawal of patients from this study are:

- Progressive disease on sunitinib treatment
- Screening failure
- The decision of a patient to withdraw from the study (i.e. if the patient withdraws informed consent)
- Administration of concomitant medication prohibited by this protocol, *Section 9.6*
- Pregnancy
- Patient is lost to follow-up
- RCC diagnosis is not confirmed by histological findings from the biopsy collected at nephrectomy or, if applicable, from confirmatory pre-study treatment diagnostic biopsy

The reason and date the patient is withdrawn from the study and subsequent planned replacement therapy will be documented in the electronic case report form (eCRF).

All patients that have received IMP must have safety evaluations for 30 days after the last dose of IMP, *Section 11.2*.

If a patient is withdrawn from further assessments, the Investigator should attempt to complete all discharge procedures, i.e. End-of Study Visit. All AEs should be followed up according to *Section 11.2*.

If a patient is withdrawn from the study, all data collected until the time of withdrawal will be used in the analyses.

Survival data (including post-study survival data if applicable) will be collected and analyzed for all patients withdrawn from the study, *Section 11.3*.

Patients randomized to Intuvax who withdraw from the study before administration of the first dose of Intuvax will be considered screening failures. Patients randomized to sunitinib alone who withdraw from the study before any assessments made at the first visit following Screening will be considered screening failures.

Only patients considered screening failures will be replaced.

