9.2 Method of Assigning Patients to Treatment Groups

At Screening the patient will be assigned a site specific screening number. This number will be generated automatically by Trial-on-Line, the electronic data capture (EDC) system used in the study. The screening number will be in the following format XX-YYYY. The letter XX is the site number and YYYY the consecutive patient number starting at 1001 at each site. The screening number will be used to identify the patient throughout trial participation.

Two (2) randomization lists are generated by [REDACTED] using a global randomization system. One (1) to be used for randomization of high-risk patients and one (1) to be used for randomization of intermediate-risk patients. One (1) copy of each randomization list is kept in a sealed envelope in a locked cabinet at [REDACTED] and one (1) copy is sent to the IWRS provider. Randomization codes will be strictly sequential within blocks as patients are eligible for randomization. The randomization code will not be available to any person involved in the conduct or evaluation of the trial before the trial database is locked.

When all results from the assessments made at Screening are available and the Investigator has confirmed eligibility and Heng-risk category for the patient the study coordinator will log into the IWRS and receive randomization and treatment information. The study nurse will make a telephone contact with the patient and inform about treatment and timing of next study visit. *NB:* If local regulations and laws require a confirmatory diagnostic biopsy before vaccination (i.e. systemic treatment) patients randomized to Intuvax will be booked for a biopsy collection visit prior to Vacc1 Visit. All participating US patients need a diagnostic pre-biopsy made at Screening in order to evaluate eligibility for sunitinib treatment following nephrectomy.

In case a patient randomized to Intuvax and sunitinib treatment withdraws prior to first dose of Intuvax or a patient randomized to sunitinib treatment only withdraws prior to any assessments made at the first visit following Screening they are considered screening failures, *Section 8.5*. A patient withdrawal contact will be performed via the IWRS allowing for additional patient inclusion until 90 patients have initiated study treatment.

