12.1.5 Primary Efficacy Analyses

Two primary endpoints are defined, each one in relation to the two primary objectives. As this trial is not powered to detect a statistically significant difference between treatment groups, *Section 12.2*, the statistical analyses described below should be considered exploratory. No adjustments for multiple testing will be done.

All patients will be followed for survival until date of death can be confirmed or up to 5 years after collection of the last patient's 18 months survival data, whichever comes first. Post-study survival data will be collected as described in *Section 11.3*. The primary analysis will be conducted based on the data collected at the entire study end. If the time point for the collection of post-study survival data at the entire study end, before DBL, differs with more than 2 months compared to the last patient's 18 months post randomization time point, then an additional collection of survival data will be conducted and the first follow-up analysis of post-study survival data will be done, as described in *Section 12.5*.

OS

The primary endpoint median OS after randomization in high-risk and intermediate-risk mRCC patients will be calculated and compared overall and by subgroup using the FAS in the following way:

Survival functions will be displayed graphically using Kaplan-Meier plots, and life table statistics will be produced including summaries of number of events and censored observations. Estimates of 25%, 50% (median) and 75% percentiles of time of survival with corresponding 95% confidence intervals will be calculated. Analysis where the survival functions will be compared between Intuvax+sunitinib, vs. sunitinib alone will be conducted using a log-rank test. Time to death in this analysis will be defined as the time from randomization until the event occurs.

In addition the primary efficacy endpoint will be evaluated using the PPS.

18-month survival rate

The primary endpoint 18-month survival rate after randomization in high-risk and intermediate-risk mRCC patients will be calculated and compared overall and by subgroup using life table statistics including summaries of number of events and censored observations and similar survival statistics as described for the analysis of OS above.

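### The primary analysis set requires 'evaluable' patients, a term neither document defines, so the plan does not secure the inclusion of randomised patients relabelled as screening failures

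*Protocol*

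**What the plan says.** **Relabelling and replacement.** Protocol 7.2.1.1 has the site telephone the patient after randomisation "in order to inform about which treatment the patient was allocated to". Protocol 8.5 then says "Patients randomized to Intuvax who withdraw from the study before administration of the first dose of Intuvax will be considered screening failures". For the other arm it says "Patients randomized to sunitinib alone who withdraw from the study before any assessments made at the first visit following Screening will be considered" screening failures; for controls that first visit is the Nephrectomy Visit. Only screening failures are replaced, and protocol 9.2 describes a withdrawal contact in the randomisation system, "allowing for additional patient inclusion until 90 patients have initiated study treatment".

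**Steps in the Intuvax arm only.** Where local rules require it, "patients randomized to Intuvax will be booked for a biopsy collection visit prior to Vacc1 Visit" (protocol 9.2). Some sites must also take an extra consent for vaccination after randomisation (protocol 7.2.1.1).

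**Analysis set.** Protocol 12.1.1 and SAP 5 both define the FAS as randomised patients who are evaluable for any efficacy endpoint. SAP 5 makes it the primary population. Neither document says what makes a patient evaluable.

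**Text that favours inclusion.** Protocol 8.5 lists screening failure among its examples of withdrawal reasons and says "Survival data (including post-study survival data if applicable) will be collected and analyzed for all patients withdrawn from the study". Protocol 12.1.5 says "All patients will be followed for survival until date of death can be confirmed", or until the end of the five-year follow-up. Protocol 7.2.1.10, on post-study survival, says "This measure is applicable for all patients". SAP 6.3.5 censors patients without a known death at the last date known alive.

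**Text that leaves exclusion open.** SAP Appendix 1 plans listing 16.2.3.1, of patients excluded from the efficacy analysis with the reason for their evaluability classification. SAP 6.2 settles set membership in a form completed before database lock and states that review of ongoing data is not blind.

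**The concern.** Both primary endpoints run from randomisation, so the comparison is protected only if every randomised patient counts in the assigned arm. Here some patients can leave after learning their allocation, lose the status of randomised patient in name, and be replaced. The event that triggers this differs between the arms. If the undefined evaluability condition were used to leave them out, the arms would lose patients by different rules, and the survival difference could move for reasons unrelated to Intuvax.

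Testing is declared exploratory, so the main risk is to the estimate. Protocol 12.2 gives adequate estimation of 18-month survival as what the sample size is expected to deliver.

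**Working it through.** **Step 1: does the text decide the question?** Follow an Intuvax patient who withdraws after randomisation and before the first dose.

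- Under protocol 8.5 the patient is a screening failure, which the same section lists as a reason for withdrawal. Survival is therefore to be collected and analysed.
- Under protocol 12.1.5 and SAP 6.3.5 the patient has at least a censored OS time.
- Under protocol 12.1.1 and SAP 5 the patient is in the FAS only if evaluable. No rule says whether a censored OS time is enough, and the 8.5 sentence does not mention the FAS.
- The safety set in SAP 5 has a checkable rule (randomised, with a safety assessment at Screening). The FAS does not.
- Protocol 11.3, to which the 8.5 sentence refers, describes complete survival collections for applicable patients, also without a definition.

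The first two lines favour inclusion; the last three leave it unsecured.

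**Step 2: what would dropping them do?** The plan gives no figure to reproduce: the sample size rests on practical considerations (protocol 12.2).

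Inputs:
- About 90 patients, 2:1, so 60 and 30 (protocol 12.2).
- *f*, the share of one randomised arm dropped: 5% or 10% (assumed).
- *S*, 18-month survival in all randomised patients: 40–60% (assumed).
- *q*, 18-month survival in those dropped: from 0 up to *S* (assumed).

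Survival in all randomised patients is a mixture, S = (1 − f)R + fq, where R is survival in those kept. The shift in that arm is therefore

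R − S = f(S − q)/(1 − f).

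| Loss in one arm | S = 40%, q = 0 | S = 60%, q = 0 | q = S |
|---|---|---|---|
| 5% | 0.05 × 0.40/0.95 = 2.1 points | 0.05 × 0.60/0.95 = 3.2 points | 0 |
| 10% | 0.10 × 0.40/0.90 = 4.4 points | 0.10 × 0.60/0.90 = 6.7 points | 0 |

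In patients, a 5% loss is 60/0.95 − 60 = 3.2 in the Intuvax arm or 30/0.95 − 30 = 1.6 in control. Losses balanced in proportion and prognosis cancel in the difference.

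**Step 3: scale.** With 60 and 30 patients and survival near 50%, the standard error of the difference is √(0.25/60 + 0.25/30) = 11.2 points. The largest shift above is 6.7/11.2 = 0.6 standard errors. As a cross-check with whole patients, take S = 50%, no true effect, and 3 of 33 randomised controls dropped with none surviving 18 months. Control survival rises from 50% to 0.50/(30/33) = 55%, and a nominal 5% two-sided test rejects 7.3% of the time.

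**Step 4: what would inclusion recover?** Suppose a share *t* of these patients is traced and the rest are censored soon after randomisation. An early-censored patient contributes almost nothing, so the effective loss is about f(1 − t). For f = 10%, the remaining shift is 0 if all are traced, 0 to 3.2 points if half are, and about 0 to 6.7 points if none are.

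**The case against.** The strongest reply is that the protocol already answers the question. Section 8.5 ties screening failure to withdrawal and withdrawal to analysis of survival. The FAS asks only for evaluability on *any* efficacy endpoint, and OS can be computed, at least as censored, for every randomised patient. Leaving these patients out would conflict with 8.5. It would also be visible: listings 16.2.3.1 and 16.2.3.2 show exclusions and evaluability, and protocol 13.9 requires the number of patients per analysis set to be reported.

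Most of this stands, and inclusion is the more natural reading. It does not close the gap. The sentence in 8.5 is absent from both FAS definitions, the SAP expects evaluability to be classified patient by patient, and visibility after the event does not fix the rule beforehand.

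On size, patients who decline a biopsy or an extra consent need not have a worse prognosis. If theirs equals that of the rest, even a one-sided loss shifts nothing. That stands, and is why each range starts at zero.

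A reader might also infer from the visit windows (Vacc1 within 28 days of Screening, control nephrectomy within 63) that the control arm would lose more patients. The documents do not support this. Both windows count from Screening, whereas relabelling can begin only at randomisation. Control nephrectomy has only a latest day. Protocol 9.1.1 puts the nephrectomy delay in the Intuvax arm at 14 to 20 days, which matches the 14 ± 3 day dosing interval plus 3 days, so control nephrectomy would fall at about the time of Vacc1. The extra Intuvax steps pull the other way.

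**Conclusion.** The point holds as an unresolved ambiguity in the primary population that should be settled before database lock. A reader might infer that the plan excludes relabelled patients from the primary endpoints. It does not say so, and protocol 8.5 read literally says the opposite. What can be said is that the definition governing the primary analysis does not carry that rule, so the passages must be reconciled.

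The effect is zero if these patients are kept and traced. If they were dropped, it would probably be modest next to the trial's imprecision, with the direction unknown. The ranges in the table rest wholly on assumed loss rates and survival, since the documents give neither, and on those dropped doing no better than the rest. Median OS would be open to the same bias but is not quantified here.

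**What to change.** - In SAP 5 and protocol 12.1.1, define the primary analysis set for OS and 18-month survival as all randomised patients, by assigned arm and randomised stratum, expressly including those labelled screening failures and replaced.
- Trace their vital status, as protocol 8.5 already requires, and censor at the last date known alive only when tracing fails.
- If an evaluable set is kept, define it and use it as a sensitivity analysis.
- Show relabelled patients by arm and reason in table 14.1.1, with the number traced.
- State that *not included* in SAP Appendix 1 means not randomised. SAP 6.3.4 bases disposition on all screened patients, table 14.1.1 on all included patients, and the appendix drops those screened but not included; these need one meaning.

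The cost is a few lines of wording and tracing for a handful of patients. Replacements already enrolled stay in, so the primary set could exceed 90: with 5% or 10% relabelled it would be 90/0.95 ≈ 95 or 90/0.90 = 100. The treatment estimate may be slightly diluted by patients who never received Intuvax. If inclusion was always intended, the change only records it.

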8.6 Premature Termination of the Study

The Investigator or the Sponsor may terminate this study prematurely for any reasonable cause. The Institutional Review Board(s) (IRBs)/Independent Ethics Committee(s) (IECs) and Competent Authorities (CAs) should be informed promptly.

Conditions that may warrant termination include, but are not limited to:

- The discovery of an unexpected, significant, or unacceptable risk to the patients enrolled in the study, or potential study patients
- A decision on the part of the Sponsor to suspend or discontinue development of Intuvax

If the CA obtains information that raises doubts about the safety or scientific validity of the clinical study, the CA can suspend or prohibit the study. Before the CA reaches its decision it shall, except where there is imminent risk, ask the Sponsor and/or the Investigator for their opinion, to be delivered within one week (Directive 2001/20/EC, Article 12, Section 1).

If the study is prematurely terminated or suspended for any reason, the Investigator/Institution should promptly inform the study patients and should assure appropriate therapy and follow-up for the patients.

8.7 Study Stopping Criteria

Study stopping criteria are defined as:

- Any death within 30 days of Intuvax administration that is not clearly attributable to surgery or disease progression
- Any CTCAE grade 4 autoimmune disorder
- Any toxicity that is unexpected, significant or unacceptable risk to the patients enrolled in the study, or potential study patients, *Section 8.6*

The identification of a study stopping criterion in a patient will result in the permanent discontinuation of Intuvax in this patient and the enrolment will be temporarily held until an appropriate evaluation of the cause of the toxicity has been determined and a correction action plan is established if needed.

The medical monitor should be notified immediately and the patient should be followed for safety as clinically indicated until the toxicity resolves and in the opinion of the investigator, no further follow-up regarding the toxicity is needed (minimum of at least 30 days after last dose of IMP).

9 TREATMENT OF PATIENTS

9.1 Investigational Medicinal Products

9.1.1 Treatment Regimens

Patients will be randomized to one (1) of the following two (2) treatment regimens:

- (i) Two (2) doses of Intuvax (10×10^6 DCs) administered intratumorally into the primary tumor 14 ± 3 days apart followed by nephrectomy and sunitinib initiated five (5) to eight (8) weeks after nephrectomy for all patients (administered dose in accordance with the SmPC/USPI)
- (ii) Sunitinib initiated five (5) to eight (8) weeks after nephrectomy for all patients (administered dose in accordance with the SmPC/USPI)

Patients randomized to Intuvax will have their first vaccination within 28 days from Screening Visit.

All patients will have nephrectomy in accordance with local practice.

Patients randomized to sunitinib only will have nephrectomy done within 63 days from Screening.

Patients randomized to Intuvax will have nephrectomy done 3 days or later after the second vaccination and within 63 days from Screening. A patient randomized to Intuvax will have a 14 to 20 day delay of Nephrectomy as compared to if the patient had been randomized to sunitinib only.

9.1.2 Identity of Investigational Medicinal Products

Intuvax

The Intuvax administered is a cryopreserved dendritic cell suspension containing 11.7×10^6 viable and HLA class II expressing cells in 1 mL heat-inactivated AB plasma, supplemented with 10% dimethyl sulfoxide (DMSO). One (1) mL Intuvax is filled in vials which are stored at -150°C or below.

The IMP is thawed at the clinical site at the time for vaccination. No preparation of the IMP prior to vaccination is needed, *Section 9.1.4*.

Sunitinib

Marketed products of sunitinib will be used in this clinical study.

9.1.3 Packaging and Labelling of Investigational Medicinal Products

All manufacturing is performed in accordance with current Good Manufacturing Practice (cGMP) and with approved license for production of cell-based advanced therapeutic medicine products.

The labelling of the primary and secondary packaging of Intuvax and the supplement label for sunitinib will be according to US investigational labelling requirement per 21 Code of Federal Regulations (CFR) 312.6, EudraLex volume 4, Annex 13 Good manufacturing practices for Medicinal products for human and veterinary use and applicable local regulatory requirements.

[REDACTED], serves as central depot and manage supply of Intuvax to all local depots and participating sites.

9.1.4 Storage, Handling and Dispensing of Investigational Medicinal Products

Intuvax

Intuvax is transported and stored at -150 °C or below in a low temperature freezer or in liquid nitrogen. [REDACTED]

A study specific manual describing all details regarding handling, transport and preparation of the IMP will be available prior to study start.

In summary, Intuvax is delivered from the manufacturer to a central depot. The central depot will subsequently deliver the Intuvax to the local depot/pharmacy (or equivalent facility) where it will be stored until vaccination.

The responsible person at the central depot will arrange for Intuvax delivery to the concerned local depot/pharmacy (or equivalent facility) upon the receipt of a randomization alert from the Interactive Web Response System (IWRS). Minimum two (2) doses of vaccine from the same batch will be shipped to the pharmacy no later than the day before the patient's first vaccination. The pharmacy or delegated person is responsible for vaccine handling prior to administration.

The vaccine will be thawed at the clinical site and administrated without any additional preparation as soon as possible after complete thawing (but no later than 60 minutes from start of thawing), *Section 9.1.5*.

Sunitinib

Sunitinib is stored at room temperature in accordance with the SmPC/USPI and local clinical practice. The patients will receive the amount needed until next planned visit with a start at the Sunitinib Start Visit. The patients will be instructed on how to administer and store sunitinib. The patients will be asked to bring all unused and empty packaging to the clinic at the next planned visit. This procedure will be repeated at all following study visits.

